2. OBJECTIVES

The objectives of this study are:

- To evaluate long-term safety and efficacy of caplacizumab
- To evaluate safety and efficacy of repeated use of caplacizumab
- To characterize long term impact of TTP

3. STUDY DESIGN

3.1. OVERALL STUDY DESIGN

3.1.1. STUDY OVERVIEW

This is a FU study for subjects who completed Study ALX0681-C301 (HERCULES) according to the protocol (i.e., completed the Final [28 day] FU visit).

The study flow chart is depicted in [Figure 4](#).

Subjects who completed Study ALX0681-C301 will be given the option to participate in this FU study and attend twice yearly (Q6M) visits for 3 years starting with a baseline visit coinciding with or scheduled to take place within 1 month after the Final (28 day) FU visit in Study ALX0681-C301^{††}. Assessments at these Q6M visits will include patient reported outcome measures, clinical assessments (including AEs, safety laboratory parameters, vital signs and physical examination), and determination of ADA, vWF:Ag (PD parameter), and disease-related markers (ADAMTS13 activity and Troponin I [TnI]).

Recurrence of TTP episode

Upon recurrence of TTP, defined as recurrent thrombocytopenia requiring initiation of daily PE, standard of care treatment consisting of daily PE and immunosuppression is to be initiated. In addition, an i.v. loading dose of open-label caplacizumab will be administered prior to initiation of daily PE^{††} followed by daily subcutaneous s.c. administration of caplacizumab for the duration of daily PE and for 30 days thereafter. Treatment with caplacizumab may be extended for a maximum of 4 weeks in case of persistent signs and symptoms of underlying disease activity (e.g., ADAMTS13 activity profile remains below 10% based on weekly measurements).

The visit schedule upon initiation of treatment consists of a recurrence visit at presentation, a visit on Day 3 of treatment with caplacizumab, weekly visits during treatment with caplacizumab (starting 1 day after the last daily PE), and a recurrence FU visit 1 week after the end of treatment with caplacizumab. At these visits, information with regard to the TTP recurrence (presenting symptoms, duration, and outcome) and treatment choice will be

^{††} Note: for subjects for whom the Final (28 day) FU visit in Study ALX0681-C301 occurred prior to local approval and site activation for this study, a time window of + 1 month after site activation is permitted to complete the screening/baseline visit.

^{††} Up to 1 PE (which may be spread over 2 or more sessions in 24 hours) may be given prior to initiation of treatment with caplacizumab as long as considered part of the PE for the treatment of the presenting TTP episode.

[figure not shown]
collected as will safety information (including AEs, safety laboratory parameters, vital signs and physical examination), and determination of PK, ADA, PD parameters (vWF:Ag and RICO), and disease-related markers (ADAMTS13 activity and TnI).

In case of recurrent thrombocytopenia requiring re-initiation of daily PE during an ongoing recurrence period (see [Figure 4](#) and [Table 2](#)), a new visit cycle is to be started, with a recurrence visit on the day of the new recurrence followed by all subsequent visits as indicated in [Table 2](#). All remaining visits of the original schedule are no longer applicable and are not to be performed.

Note: an i.v. loading dose of caplacizumab needs to be administered prior to re-initiation of PE for the recurrence.

Q6M visits that are scheduled within a recurrence period will not be held as assessments at such visits would be confounded by the concurrent recurrence.

Note: Treatment with caplacizumab may not be initiated for subjects who do not fulfil the caplacizumab treatment criteria (see section [3.2.3](#)). Hence, these subjects will be treated with standard of care only. The visit schedule in case of initiation of only standard of care treatment includes a recurrence visit at presentation and a recurrence FU visit at 30 days after end of daily PE (see [Appendix 1](#) for schedule of assessments).

M: month; Y: year

Figure 4: Study flow of Study ALX0681-C302.

Treatment in case of recurrence:

Standard of care treatment (per standard site practice) can include:

- PE with plasma (e.g., fresh frozen plasma, solvent detergent/viral-inactivated plasma, cryosupernatant)
- Corticosteroid treatment
- Use of other immunosuppressive agents (e.g., rituximab)

Initiation of treatment with caplacizumab^{§§}:

Daily PE period

- Loading i.v. dose: subjects will receive a single loading dose of 10 mg study drug by i.v. bolus injection from 6 hours to 15 minutes prior to start of daily PE treatment^{***}.
- Daily s.c. dose: within 2 hours after completing each daily PE, a s.c. injection of 10 mg study drug will be administered daily throughout the full duration of PE treatment.

30-day post-daily PE period

Daily s.c. administration of 10 mg study drug will continue for a period of 30 days after stop of daily PE. No adjustment to this period will be made for tapering of PE. Subjects (and/or caregivers) will be trained on preparing and administering caplacizumab and are to administer the study drug after discharge from the hospital.

Treatment extension period

Treatment with caplacizumab beyond these 30 days will be guided by a number of risk factors for relapse of the presenting TTP episode and may be accompanied by an optimization of the immunosuppressive treatment. The risk factors will include the ADAMTS13 activity profile, as well as other signs and symptoms of continued underlying disease activity, such as presence of inhibitors if measured as routine practice by the site. Continued caplacizumab treatment should be given for additional 7-day periods with a maximum of 28 days for subjects whose ADAMTS13 activity profile remains below 10% based on weekly measurements and/or exhibit other clinical signs or symptoms of underlying disease. caplacizumab treatment should be stopped when ADAMTS13 activity shows a sustained upward trend of >10% and/or when there is an improvement in other signs and symptoms of underlying disease activity and at the latest on Day 28 of the study drug treatment extension period.

Estimated Study Duration

The anticipated study duration per subject is approximately 3 years. The end of the study is defined as the last visit of the last subject participating in the study.

^{§§} Pregnant subjects or those with a history of a severe and/or serious hypersensitivity reaction to caplacizumab may participate in the study but will not receive treatment with caplacizumab. Also, treatment with caplacizumab may not be initiated for subjects who did not have a baseline visit.

^{***} Up to 1 PE (which may be spread over 2 or more sessions in 24 hours) may be given prior to initiation of treatment with caplacizumab as long as considered part of the PE for the treatment of the presenting TTP episode.

Determination of Sample Size

The sample size is not based on statistical considerations but rather on the number of subjects who complete Study ALX0681-C301 (HERCULES) and accept the option to participate in this FU study (ALX0681-C302). All subjects who enrolled in this FU study will be included in the safety and efficacy analyses.

Independent Data and Safety Monitoring Board (DSMB)

The sponsor will appoint a DSMB consisting of an independent group of clinical experts who are not participating in the study. They will be supplemented by an independent statistician. The objective of the DSMB will be to review the safety data. The DSMB meetings will be convened every year. This is to review the SAE and mortality information (including the overall number of subjects treated up to that point, rates, and subject-level details). Ad hoc meetings will be determined by the DSMB based on incidence of SAEs. The DSMB will advise the sponsor concerning continuation, modification or termination of the study after every meeting.

The composition, objectives, and role and responsibilities of the independent DSMB will be described in a DSMB charter, agreed with the DSMB members and Sponsor. The DSMB charter will also define and document the content of the safety summaries, and general procedures (including communications).

3.1.2. BLINDING

Not applicable. Upon a recurrence of TTP all subjects will receive open-label treatment with caplacizumab in addition to standard of care.

3.2. SELECTION OF STUDY POPULATION

Subjects who completed Study ALX0681-C301 (HERCULES) will be given the option to participate in this follow-up Study ALX0681-C302.

3.2.1. INCLUSION CRITERIA

Each potential subject must satisfy all of the following criteria to be enrolled in the study:

1. Completed the Final (28 day) FU visit in Study ALX0681-C301.
2. Is ≥ 18 years of age at the time of signing the informed consent form (ICF).
3. Provided informed consent prior to initiation of any study specific activity/procedure.

3.2.2. EXCLUSION CRITERIA

The criteria for exclusion are the following:

1. Not being able/willing to comply with the study protocol procedures.
2. Currently enrolled in a clinical study with another investigational drug or device.

3.2.3. CAPLACIZUMAB TREATMENT CRITERIA

Initiation of treatment with caplacizumab is for subjects with a clinical diagnosis of an episode of recurrent acquired TTP requiring initiation of daily PE treatment and who had a baseline visit.

Treatment with caplacizumab is not permitted for subjects who:

1. Are pregnant or intend to get pregnant in the near future (check on use of contraceptives, see section [3.3.7](#)).
2. Have a history of a severe and/or serious hypersensitivity reaction to investigational medicinal product (IMP) in Study ALX0681-C301 or Study ALX0681-C302.

3.2.4. REMOVAL OF SUBJECTS FROM THERAPY OR ASSESSMENT

3.2.4.1. WITHDRAWAL OF SUBJECTS FROM THE STUDY

Participation in the study is strictly voluntary. A subject has the right to withdraw from the study at any time, for any reason. In case of withdrawal, an Early Termination Visit will be done. Note: no further assessments/visits will be done in case subjects terminate study participation for reasons of lost to follow-up or informed consent withdrawal.

In the event a subject is discontinued from the study, the Medical Monitor is to be informed.

3.2.4.2. CRITERIA FOR STUDY DRUG TREATMENT DISCONTINUATION

Temporary discontinuation of study drug should be considered in cases where the subject develops severe or serious bleeding. All subjects in the study experiencing bleeding events should be treated using the standard medical and/or surgical intervention (also see section 3.3.6). Treatment with study drug should only be restarted when the bleeding has stopped.

Note: vWF preparations can be used as antidote to caplacizumab if needed. vWF and FVIII preparations as combination products are commercially available.

Permanent discontinuation of study drug should be considered in cases where the subject develops:

- a severe hypersensitivity reaction, as discussed with Sponsor/Medical Monitor
- severe (including life-threatening) bleeding requiring urgent medical and/or surgical intervention which is accompanied by significantly low vWF and/or FVIII levels which are slow to respond to study drug interruption and replacement therapy

Study drug must be permanently discontinued if any of the following occurs:

- Pregnancy
- If the Investigator deems it is in the subject's best interest

Subjects who have to discontinue study drug but who have not been permanently discontinued from the study, should proceed with the Q6M visits and/or the recurrence visit schedule as originally planned to perform the assessments as specified in the [Schedules of Assessments](#).

3.2.4.3. STUDY TERMINATION

If the Sponsor abandons the study prior to commencement of any protocol activities, and/or after IEC/IRB and CA approvals have been received, the Investigator or Sponsor must notify the IEC/IRB and CA by letter outlining the reasons for abandonment of the study, as required per national regulations.

At any time during the study, the Sponsor may suspend or terminate the study or part of the study for any reason. If the Investigator plans to suspend or terminate participation in the study, the Investigator will promptly inform the Sponsor and the IEC/IRB and provide them with a detailed written explanation.

Upon study completion, the Sponsor will provide the Investigator, IEC/IRB, and CA with final reports and summaries as required by regulations.

In case of suspension or halt due to safety reasons, the CA and IEC/IRB will be notified immediately and at the latest within the number of days as specified by local regulations after the study is halted, clearly explaining the reasons, and describe follow-up measures, if any, taken for safety reasons.

3.3. TREATMENT OF SUBJECTS

3.3.1. OVERVIEW OF TREATMENTS ADMINISTERED

Upon each recurrence of TTP, open-label caplacizumab in addition to standard of care therapy should be initiated. Caplacizumab should be administered daily at least for the duration of daily PE and for 30 days thereafter. Treatment with caplacizumab may be extended for a maximum of 4 weeks in case of persistent signs and symptoms of continued underlying disease activity.

Note: Initiation of treatment with caplacizumab is not allowed in case of pregnancy and for subjects with a history of severe and/or serious hypersensitivity to IMP in Study ALX0681-C301 or Study ALX0681-C302. In addition, treatment with caplacizumab may not be initiated for subjects who did not have a baseline visit. Also see section 3.2.3.

Standard of care treatment (per standard site practice) can include:

- PE with plasma (e.g., fresh frozen plasma, solvent detergent/viral-inactivated plasma, cryosupernatant)
- Corticosteroid treatment
- Use of other immunosuppressive agents (e.g., rituximab)

Initiation of treatment with caplacizumab (in addition to standard of care):

Daily PE period

- Loading i.v. dose: subjects will receive a single loading dose of 10 mg study drug by i.v. bolus injection from 6 hours to 15 minutes prior to start of daily PE treatment. Up to 1 PE (which may be spread over 2 or more sessions in 24 hours) may be given prior to initiation of treatment with caplacizumab as long as considered part of the PE for the treatment of the presenting TTP episode.
- Daily s.c. dose: within 2 hours after completing each daily PE, a s.c. injection of 10 mg study drug will be administered daily throughout the full duration of PE treatment.

30-day post-daily PE period

Daily s.c. administration of 10 mg study drug will continue for a period of 30 days after stop of daily PE. No adjustment to this period will be made for tapering of PE. After discharge from hospital, subjects are allowed to self-administer (after learning how to prepare and s.c. inject the study drug). Towards the end of the daily PE period and when hospital discharge is foreseen, subjects (or caregiver) should be trained in the s.c. administration of the study drug under the supervision of the Investigator or designee to allow for administration when

at home. After discharge from hospital, subjects or caregiver will need to be able to administer s.c. study drug. For more details, please refer to section 3.3.6.

Treatment extension period

Treatment with caplacizumab beyond these 30 days will be guided by a number of risk factors for relapse of the presenting TTP episode and may be accompanied by an optimization of the immunosuppressive treatment. Caplacizumab should be extended for additional 7-day periods up to a maximum of 28 days for subjects who in the opinion of the Investigator have persistent active underlying disease. In parallel, optimization of the immunosuppressive treatment may be considered and includes reversal of corticosteroid tapering through increase or re-initiation of corticosteroid treatment, or start/continuation of other immunosuppressive treatment such as rituximab (as per standard site practice).

Decision on treatment extension

The decision to extend treatment with additional 7-day periods should be made by the Investigator based on the ADAMTS13 activity profile, as well as other signs and symptoms of continued underlying disease activity, such as presence of inhibitors if measured as routine practice by the site.

ADAMTS13 activity will be measured weekly and results of these analyses will be communicated to the clinical sites upon availability.

Caplacizumab treatment should be stopped when ADAMTS13 activity shows a sustained upward trend of >10% or is stable and there are no other signs and symptoms of disease activity, and at the latest on Day 28 of the study drug treatment extension period.

Recurrences during the Recurrence Period

In case of recurrent thrombocytopenia requiring re-initiation of daily PE during an ongoing recurrence period (see [Figure 4](#) and [Table 2](#)), a new visit cycle is to be started, with a recurrence visit on the day of the new recurrence followed by all subsequent visits as indicated in [Table 2](#). All remaining visits of the original schedule are no longer applicable and are not to be performed.

Note: an i.v. loading dose of caplacizumab needs to be administered prior to re-initiation of PE for the recurrence.

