Treatment with caplacizumab beyond these 30 days will be guided by a number of risk factors for relapse of the presenting TTP episode and may be accompanied by an optimization of the immunosuppressive treatment. The risk factors will include the ADAMTS13 activity profile, as well as other signs and symptoms of continued underlying disease activity, such as presence of inhibitors if measured as routine practice by the site. Continued caplacizumab treatment should be given for additional 7-day periods with a maximum of 28 days for subjects whose ADAMTS13 activity profile remains below 10% based on weekly measurements and/or exhibit other clinical signs or symptoms of underlying disease. Caplacizumab treatment should be stopped when ADAMTS13 activity shows a sustained upward trend of >10% and/or when there is an improvement in other signs and symptoms of underlying disease activity and at the latest on Day 28 of the study drug treatment extension period.

Study population:

Subjects who completed Study ALX0681-C301 (HERCULES) will be given the option to participate in this follow-up study.

[‡] Pregnant subjects or those with a history of a severe and/or serious hypersensitivity reaction to caplacizumab may participate in the study but will not receive treatment with caplacizumab. Also, treatment with caplacizumab may not be initiated for subjects who did not have a baseline visit.

[§] Up to 1 PE (which may be spread over 2 or more sessions in 24 hours) may be given prior to initiation of treatment with caplacizumab as long as considered part of the PE for the treatment of the presenting TTP episode.

Number of subjects:

All subjects enrolled in Study ALX0681-C301 are eligible to participate in Study ALX0681-C302.

Inclusion criteria:

Each potential subject must satisfy all of the following criteria to be enrolled in the study:

1. Completed the Final (28 day) FU visit in Study ALX0681-C301.
 2. Is ≥ 18 years of age at the time of signing the informed consent form (ICF).
 3. Provided informed consent prior to initiation of any study specific activity/procedure.
-

Exclusion criteria:

The criteria for exclusion are the following:

1. Not being able/willing to comply with the study protocol procedures.
 2. Currently enrolled in a clinical study with another investigational drug or device.
-

Caplacizumab treatment criteria:

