1.1.1. TREATMENT OF ACQUIRED TTP

Plasma exchange (PE) is the current standard of care for treatment of acquired TTP. PE replenishes ADAMTS13, partially normalizing vWF processing, and removes pathogenic autoantibodies. Daily exchanges are to continue for a minimum of 2 days after the platelet count has normalized [12]. Immunosuppression, most commonly in the form of corticosteroids is often started together with PE to reduce the production of autoantibodies. Despite standard of care treatment, an exacerbation occurs in approximately 30% of patients within 30 days of stopping PE [13]. Severe ADAMTS13 deficiency (<10%) has been identified as a potential biomarker of active underlying disease and an elevated risk of relapse in these patients [14, 15].

In spite of recent advances in understanding the disease, there are no approved pharmacologic therapies for acquired TTP. Caplacizumab represents a novel approach to treating the microthrombotic component of acquired TTP. Caplacizumab is being developed with the aim of preventing platelet consumption and formation of further microthrombi thereby reducing the duration of tissue ischemia and protecting the patient from the manifestations of the disease while the underlying process resolves. When used in conjunction with PE for initial and recurrent episodes of acquired TTP, its ability to prevent further microthrombus formation may translate into better long term outcomes for these patients.

[figure not shown]

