1.2.5. SAFETY PROFILE AND RISK ASSESSMENT

The benefit and risk assessment for administration of caplacizumab, as detailed in the Investigator's Brochure, supports initiation of the proposed clinical study.

Overall, Study ALX-0681-2.1/10 (TITAN study) provided evidence for the clinical efficacy of caplacizumab as potential treatment for patients with acquired TTP who were receiving standard of care therapy, with respect to reducing the time-to-response (based on confirmed recovery in platelet counts) and reducing the incidence of exacerbation during treatment. These findings were associated with tangible clinical benefits in terms of reduced mortality/morbidity [17]. The higher incidence of relapse soon after discontinuation of caplacizumab appeared to be associated with persistent low ADAMTS13 activity (<10%), suggesting unresolved underlying auto-immune activity. Study ALX0681-C301 and this study will evaluate whether such patients would benefit from continuing treatment with caplacizumab for a longer period after discontinuation of PE.

The safety results in the TITAN study revealed no unexpected findings in relation to AEs. The main safety finding associated with caplacizumab treatment was an increase in bleeding-related AEs, which was consistent with findings in previous studies and is an expected consequence of the pharmacological activity of the drug. Notwithstanding this, the majority of bleeding events in the study were mild to moderate in severity, and an equal number of subjects in each treatment arm (2 subjects per arm) had a serious bleeding related TEAE. Hence, bleeding risk appears to be acceptable in the context of the clinical benefits of caplacizumab in the TTP indication. Nonetheless, vWF preparations can be used as antidote to caplacizumab if needed. vWF and FVIII preparations as combination products are commercially available.

With regard to immunogenicity, taking into account patient, product and disease related factors, caplacizumab was assigned a low risk class designation. In the TITAN study, drug induced TE antibodies were detected in 9% of caplacizumab treated subjects. No immunogenicity related safety findings were reported. Whether retreatment with caplacizumab includes a risk for inducing ADA is currently unknown.

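### The caplacizumab stop sentence in Protocol 3.3.1 sets no level for stable ADAMTS13, so read literally it stops drug in a patient stable below 10% with no other signs, whom the synopsis, Protocol 3.1.1 and SAP 1.4 say to keep treating

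*Protocol*

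**What the plan says.** Two versions of the extension and stop rule are in force.

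**Protocol 3.3.1 (Treatment extension period; Decision on treatment extension).** Treatment is extended in 7-day periods, up to 28 days, "for subjects who in the opinion of the Investigator have persistent active underlying disease". No ADAMTS13 cut-off is attached. "The decision to extend treatment with additional 7-day periods should be made by the Investigator based on the ADAMTS13 activity profile", together with other signs and symptoms. Treatment should be stopped on a sustained upward trend of more than 10%, "or is stable and there are no other signs and symptoms of disease activity", and by extension Day 28 at the latest.

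**Synopsis, Protocol 3.1.1 and SAP 1.4 (Treatment extension period).** These three share one text. Continued treatment should be given in 7-day periods, up to 28 days, "for subjects whose ADAMTS13 activity profile remains below 10% based on weekly measurements and/or exhibit other clinical signs or symptoms of underlying disease". Treatment should be stopped on a sustained upward trend of more than 10% "and/or when there is an improvement in other signs and symptoms of underlying disease activity", again by Day 28. This stop sentence has no limb for stable activity.

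Elsewhere the protocol treats activity below 10% as a warning. Section 1.1.1 says that severe deficiency (below 10%) "has been identified as a potential biomarker of active underlying disease". Sections 3.1.1 and 3.4.1.3 give a profile remaining below 10% as their example of persistent disease activity. Section 1.2.5, referring to patients with persistently low activity, says the parent study and this one "will evaluate whether such patients would benefit from continuing treatment with caplacizumab for a longer period after discontinuation of PE".

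**The concern.** A site that works from 3.3.1, the treatment section, finds no 10% threshold for extending and a stop sentence that a patient flat at, say, 5% satisfies if nothing else is wrong. A site that works from the synopsis or 3.1.1 finds that the same patient should go on.

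The protocol's own background shows why this patient matters. In the phase II caplacizumab arm (Protocol 1.2.4), 7 of 8 first-month relapses came 4 to 10 days after stopping drug, and all 7 patients had activity below 10% at baseline, during and near the end of treatment. These data are few and uncontrolled, but they are the reason the extension exists. A stop sentence followed as written would withdraw drug from the group that 1.2.5 says the study will evaluate.

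For the analysis, the reported extension percentage and exposure duration (SAP 2.4.3.1) would partly reflect which section a site had read.

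**Working it through.** **1. Apply each text to three patients at the end of the 30 days after daily PE.**

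| Patient | Protocol 3.3.1 stop sentence | Synopsis, 3.1.1, SAP 1.4 |
|---|---|---|
| A. Flat at 5%, never any other signs | Stable and no other signs: stop | Below 10%: continue. No upward trend and no other signs that could improve, so the stop sentence is not met |
| B. Flat at 5%, other signs improved but still present | Other signs remain, so the stable limb is not met | Continue limb met (below 10%) and stop limb met (improvement): both apply |
| C. Stable at or above 10%, no other signs | Stop | Continue limb not met |

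The instructions are opposite for patient A. For patient B, the synopsis text conflicts with itself. For patient C there is no conflict. The problem is confined to activity below 10%.

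**2. Does the grammar of 3.3.1 rescue it?** The sentence has the form X or Y and Z, where X is the upward trend, Y is stable and Z is no other signs. For patient A, X is false and Y and Z are true. Read as (X or Y) and Z, the result is stop. Read as X or (Y and Z), the result is also stop. Only a level attached to Y changes the answer.

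**3. Dose range per affected episode.** Inputs: 30 daily doses after daily PE, extension in 7-day periods to a maximum of 28 days, 10 mg per dose (Protocol 3.3.1). Doses after daily PE with k extension weeks = 30 + 7k.

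| k | Doses | Ratio to 30 | Total |
|---|---|---|---|
| 0 | 30 | 1.000 | 300 mg |
| 1 | 37 | 1.233 | 370 mg |
| 2 | 44 | 1.467 | 440 mg |
| 3 | 51 | 1.700 | 510 mg |
| 4 | 58 | 1.933 | 580 mg |

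**4. Adverse event window.** The recurrence follow-up visit falls 7 (±1) days after treatment ends (Protocol Table 2) and closes the recurrence period (SAP 2.1.4). SAP 2.4.5.1 limits the recurrence-population tables to that period.

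- Without extension: 30 + 7 = day 37 after daily PE (36 to 38).
- Full extension: 58 + 7 = day 65 (64 to 66).

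The residual treatment epoch in SAP 2.1.4 (last dose + 30 days) would on its own give day 60 versus day 88, but the limit in 2.4.5.1 applies first. Either way the difference is at most 28 days.

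**5. What is not touched.** Caplacizumab in this study is given only after a recurrence. Time to first recurrence (SAP 2.1.3.5.5), the proportion with any recurrence, and the group-wise efficacy analyses, which stop at the first recurrence (SAP 2.4.4), cannot depend on how long a recurrence was treated.

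**The case against.** The best defence is that 3.3.1, read as a whole, points the right way. The Investigator extends for persistent active disease, and the ADAMTS13 profile is the first thing to be weighed. The rest of the protocol says what activity below 10% means, so an Investigator would have to disregard that to stop at a flat 5%. *Stable* plausibly means stable above 10%. Summary sentences in the synopsis, 3.1.1, 3.3.1 and 3.4.1.3 also say that treatment *may* be extended, so some variation between sites is intended and one rule would not remove it. This stands in part: it makes the literal reading less likely. It does not remove the conflict, because 3.3.1 has a separate sentence saying that treatment should be stopped and the other three places say that it should be given.

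It also stands that the outputs are descriptive and follow actual dosing. The SAP plans no comparison of extended with non-extended patients, and the adverse event overviews include incidence per 100 person-months (SAP 2.4.5.1), which allows in part for unequal observation time.

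Three stronger readings are tempting and are not supported:

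- A reader might infer that 3.3.1 stops drug whenever ADAMTS13 is stable. The stable limb also requires that there be no other signs or symptoms.
- A reader might infer that the sponsor means to stop patients below 10%. Protocol 1.1.1, 1.2.4, 1.2.5, 3.1.1 and 3.4.1.3 point the other way.
- A reader might take 30 versus 58 doses as the size of an error. It is the range the protocol permits for any patient, and nothing in the documents says how many patients would be in this state.

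**Conclusion.** The concern holds as a conflict of wording in a rule that sets dosing duration. For a patient stable below 10% with no other signs, the literal stop sentence in 3.3.1 and the continue sentence in the synopsis, 3.1.1 and SAP 1.4 give opposite instructions. It should be fixed, mainly for patient safety.

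The difference is 0 to 28 daily doses per affected episode, and at most 28 days in the window for recurrence-population adverse events. The affected outputs are the percentage with an extension, exposure duration and that window. None is miscalculated. No effect on relapse is estimated, and the documents do not support one.

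This rests on two assumptions: that *other signs* means signs other than ADAMTS13, as the preceding text in 3.3.1 implies, and that some sites would act on 3.3.1 alone.

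**What to change.** - **Protocol 3.3.1:** insert *at or above 10%* directly after *stable*, keeping the condition on other signs. This alone resolves patient A.
- **Synopsis, Protocol 3.1.1 and SAP 1.4:** align the stop sentence so that improvement in other signs does not by itself stop treatment while ADAMTS13 remains below 10%. This goes beyond wording, because it removes an existing stop trigger, so the sponsor should confirm the clinical content.
- **While the text is open:** say whether the upward trend of more than 10% means an increment or a level, and whether the condition on other signs applies to both limbs in 3.3.1.
- **Keep** the Investigator's decision and the Day 28 limit.

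The cost is a protocol wording amendment, which may need ethics committee and competent authority approval if judged substantial (Protocol 4.1), matching SAP text and a site clarification. No patients, visits or data items are added.

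The SAP plans database lock for December 2020. If recurrence treatment is already complete, the protocol edit can no longer change dosing. The SAP text should then be corrected and the study report should say that the extension data arose under two wordings.
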